To have an unbiased sampling frame, the study population for the morbidity study will consist of those identified by computerized databases from the DMDC and ATSDR as having lived or worked at Camp Lejeune during the period of drinking water contamination. The study population will also include active duty Marines and civilian employees randomly sampled from those stationed or employed at Camp Pendleton anytime during June 1975-December 1985 and December 1972-December 1985, respectively, and who were not stationed at Camp Lejeune during the period of drinking water contamination. This comparison sample from Camp Pendleton will total 50,000 Marines and 10,000 civilians.

RISK ASSESSMENTS AND DRINKING WATER STANDARDS

The MCLs for TCE, PCE, and benzene are 5 ppb (or 5 µg/L); the MCL for vinyl chloride is 2 ppb; and the MCL for DCE is 100 ppb. The EPA calculated 10^{-6} cancer risk for TCE, vinyl chloride and benzene are 3 ppb, 0.02 ppb, and 1 ppb, respectively. California has set public health goals (PHGs) for these contaminants based on their carcinogenicity (in animals and/or humans), or in the case of DCE, non-cancer endpoints

(California Environmental Protection Agency 1999, 2000, June 2001, August 2001). The PHGs based on carcinogenicity correspond to a 10^{-6} cancer risk. The PHGs for TCE, PCE, vinyl chloride, and benzene are 0.8 ppb (mice liver tumors), 0.06 ppb (liver cancer in mice, leukemia in rats), 0.05 ppb (lung cancer in mice), and 0.15 ppb (leukemia among workers). The PHG for DCE is 60 ppb based on kidney and liver effects in mice. For chronic, non-cancer endpoints, the PHGs for TCE, PCE, vinyl chloride and benzene are 1000 ppb (kidney effects in rats), 11 ppb (neurobehavioral effects in humans), 3 ppb (liver effects in rats) and 26 ppb (hematological effects in refinery workers).

LITERATURE REVIEW ON HEALTH EFFECTS OF VOC-CONTAMINANTS

Chronic Adult Health Effects of the VOC-Contaminants

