participation rate may have minimal selection bias (Groves 2006; Galea and Tracy 2007). Moreover, published mail survey studies have widely varying response rates which are likely due to differences in population surveyed and by survey administration methods. In the early 1990s, a 60% response rate for mail surveys was suggested as a “standard for acceptability” (Evans et al. 2004). One review of 13 mailed health surveys conducted prior to 2005 estimated an average response rate of 65% (Rosoff et al. 2005; Nakash et al. 2006). A recent meta-analysis of 39 mailed surveys obtained an average response rate of 45% with a range of response rates of 10% to 89% (Shih and Fan 2008). Given that recent mailed health surveys of military populations have achieved response rates of between 30% and 40% (Kang et al. 2009; Ryan et al. 2007), a realistic goal for the study may be to achieve a participation rate of at least 40%.

Exposure Assessment

Owing to the paucity of historical, contaminant-specific data, the exposure assessment will consist of an historical reconstruction of the spatial and temporal distribution of the contaminant-specific compounds at locations (such as residences or worksites) serviced by a water distribution system using ground water fate and transport and distribution system models. This historical reconstruction modeling is being conducted for the study “Exposure to Volatile Organic Compounds in Drinking Water and Specific Birth Defects and Childhood Cancers at United States Marine Corps Base Camp Lejeune, North Carolina”. The modeling will provide monthly average estimates (and monthly Monte Carlo simulated 95% interval ranges) of the concentrations of contaminant-specific compounds in drinking water delivered to study subject residences or worksites. Information collected in the survey, as well as information on the areas and family housing

units served by each drinking water system, the locations where units were barracked, family housing records, and location of worksites will be used to assign exposures.

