For a sample size calculation, the values of the alpha error, beta error, and minimum meaningful effect size are selected, and the required sample size is calculated. However, since the number of exposed subjects cannot be increased, and the alpha and beta errors should be set as low as possible, the only parameter that can vary is the meaningful effect size. Table 1 provides estimates of the minimum meaningful effect size (i.e., the incidence rate ratio or “RR”) for various cancers assuming an alpha error of 0.10 (i.e., equivalent to using a 90% confidence interval), a beta error of 0.10 (i.e., 90% statistical power), and various estimates of exposure prevalence in the surveyed population. The expected number of cancers provided in Table 1 are based on the age-specific 1999-2004 U.S. cancer incidence rates (all genders and race/ethnicity groups combined) from the National Program of Cancer Registries and estimates of the person-time contributed to each 5-year age grouping by the surveyed population after a 10-year lag to account for a latency period. The table assumes that the survey is sent to 247,000 from Camp Lejeune and 60,000 from Camp Pendleton and that the overall response rate for the survey is 65%. For most cancers, the minimum detectable RR is less than 2.0.

Reimbursement

No remuneration will be offered to participants.

Human Subjects and Confidentiality

The Centers for Disease Control and Prevention (CDC) and ATSDR Privacy Act

Officer has reviewed this Institutional Review Board (IRB) application and has determined that the Privacy Act is applicable. The contractor must verify full names and locating information on respondents because certain information (date of birth, social security number) must be verified or obtained in order to conduct the study and analyze the data. Privacy Act clauses will be included in the contract to protect against inappropriate data disclosures. Records will become part of the ATSDR Privacy Act system of records 09-19-0001, "Records of Persons Exposed or Potentially Exposed to Toxic or Hazardous Substances."

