All electronically entered information obtained from surveys will be reviewed for missing data and ambiguous responses. Internal consistency and validity programs will be used to identify and correct coding and data entry errors. The web-based survey will include prompts to alert participants if they incorrectly answer or skip questions; drop down boxes that present ranges of possible answers; and electronic skip patterns that automatically skip irrelevant questions.

Data Analysis

The civilian employees will be analyzed separately from the active duty personnel

and their dependents. This is because the primary exposure to drinking water contaminants for the civilian employees is not the residence, but the workplace location. If the exposure-response relationship for a specific condition in the analysis of civilian employees is observed to be similar to that observed in the analysis of active duty personnel and their dependents, then a combined analysis may be conducted.

In the analysis of active duty personnel and their dependents, there are no dependents from Camp Pendleton. It will be assumed that dependents and active duty personnel with similar residential drinking water exposures (including no exposure) will have similar risks for a condition. In subsequent analyses, effect modification of the exposure-response relationship for a specific condition by whether the respondent was a dependent or active duty personnel will be explored.

Person-time will accumulate from the date the person first resided or worked at Camp Lejeune (or Camp Pendleton) until date of death or the date that the health surveys are mailed. The monthly average levels of contaminants in the drinking water will be used to estimate exposure. The exposure intensity (average and maximum exposure level), exposure duration, and cumulative exposure measures will be calculated. In addition, these exposure measures will be categorized using a priori meaningful cutpoints and/or quantiles based on the exposure distribution of respondents from Camp Lejeune, and cutpoints from a smoothing procedure (e.g., splines or LOESS). The monthly Monte Carlo 95% interval range for each contaminant will be taken into account during the categorization of exposure variables.

The analyses will focus on reported diseases of interest that are confirmed by medical record, death certificate, or cancer registration. However, because medical

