
World Health Organization (WHO). Trichloroethene in Drinking-water: Background document for development of WHO Guidelines for Drinking-water Quality. 2005.

DRAFT

Table 1. Minimum Detectable Incidence Rate Ratio (“RR”)

% disease in the unexposed	Cancers*	10% unexposed**	20% unexposed**	25% unexposed**	30% unexposed**
.08%	Brain, Leukemias	1.62	1.57	1.56	1.55
.22%	Colon & Rectum	1.35	1.33	1.32	1.32
.02%	Esophagus, Larynx, Multiple Myeloma	2.43	2.32	2.29	2.26
.09%	Kidney, Oral	1.58	1.53	1.52	1.51
.03%	Liver	2.11	2.02	2.00	1.98
.20	Lung, Thyroid	1.37	1.34	1.34	1.33
.24%	Melanoma	1.33	1.31	1.30	1.30
.16%	Non-Hodgkin’s lymphomas	1.42	1.39	1.38	1.37
.04%	Pancreas, Stomach	1.93	1.86	1.84	1.82
.06%	Urinary Bladder	1.73	1.67	1.66	1.65

* More than one cancer type may have the same estimated incidence in the unexposed.

** % unexposed among those who resided, worked or were stationed at Camp Lejeune. This group is then added to those who were stationed at Camp Pendleton. For example, assuming 247,000 from Camp Lejeune and 60,000 from Camp Pendleton, and assuming a 65% participation rate, then approximately 160,550 from Camp Lejeune and 39,000 from Camp Pendleton will respond to the survey. The “10% unexposed” includes the 39,000 from Camp Pendleton and 10% of the Camp Lejeune participants (i.e., 16,055), for a total of 55,055 unexposed.

The **minimum detectable risk ratio** was calculated based on a type 1 error of .10 (equivalent to a 90% confidence interval or a p-value, two-tailed of .10) and a type 2 error of .10 (equivalent to 90% statistical power).

The incidences in the unexposed group were estimated based on the age-specific, 1999-2004 U.S. cancer incidence rates (all genders and race/ethnicity groups combined) from the National Program of Cancer Registries, CDC and the following assumptions:

1. The health survey instrument would be mailed to approximately 307,000 including 60,000 from Camp Pendleton;
2. Participation rate would be 65%
3. The average participant first resided or worked at the base at age 19 in 1980. (This assumption is based on the fact that the majority of those receiving the survey were active duty Marines and Navy personnel who were stationed at the base anytime between 1975 and 1985 and who started active duty in 1975 or later.)
4. Follow-up begins 10 years after first resided or stationed at the base (i.e., a 10-year latency period)

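### Table 1's detectable rate ratios hold only for 65% participation and one pooled analysis; at the protocol's own 40% goal, power at those ratios is about 70-77%, not 90%, and the separate analyses have no figures

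*Protocol*

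**What the plan says.** The power section assumes 247,000 surveys sent for Camp Lejeune and 60,000 for Camp Pendleton "and that the overall response rate for the survey is 65%. For most cancers, the minimum detectable RR is less than 2.0". It and Table 1 use a two-sided type 1 error of 0.10 ("equivalent to a 90% confidence interval or a p-value, two-tailed of .10") and "a type 2 error of .10 (equivalent to 90% statistical power"). Assumption 2 under Table 1 reads "Participation rate would be 65" percent. The table note turns this into 160,550 Lejeune and 39,000 Pendleton respondents. All respondents enter one exposed-versus-unexposed contrast, and each column adds an assumed unexposed share of Lejeune (10% to 30%) to the whole Pendleton sample.

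Three other places in the protocol bear on this:

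- **Expert Panel:** after citing 30% to 40% for recent military mail surveys, it says "a realistic goal for the study may be to achieve a participation rate of at least 40" percent. The same section has the panel base its recommendations on how to proceed partly on the power calculations.
- **Data Analysis:** "The civilian employees will be analyzed separately from the active duty personnel" and their dependents. A combined analysis may follow if the exposure-response relationships look similar. Unexposed Lejeune residents join the Pendleton reference group if their risk is similar; otherwise an indicator variable keeps them apart.
- **Study Objectives:** "This comparison sample from Camp Pendleton will total 50,000 Marines and 10,000 civilians".

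**The concern.** The only detectable effects in the protocol rest on a participation rate 25 percentage points above the goal that the protocol calls realistic. They also rest on a pooled contrast that the analysis section makes optional. No figure is given at 40% or 30%, for active duty with dependents alone, or for civilians alone.

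The expert panel is asked to use the power calculations when it advises on continuing, and Table 1 is the only calculation in the protocol. Several cancers with the weakest power (liver, pancreas, esophagus, multiple myeloma) are named diseases of interest.

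**Working it through.** **Inputs.** Two-sided alpha 0.10 (z = 1.6449) and power 0.90 (z = 1.2816). Mailings are 247,000 and 60,000. Baseline risks p0 are the first column of Table 1. With response rate f and unexposed Lejeune share u:

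- unexposed n0 = f × (60,000 + u × 247,000)
- exposed n1 = f × (1 − u) × 247,000
- r = n1/n0

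**Formula.** The protocol names none. A two-proportion comparison with Fleiss continuity correction fits Table 1 best. With p1 = RR × p0, d = p1 − p0 and p̄ = (p0 + r·p1)/(1 + r):

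- n = [1.6449·√((1 + 1/r)·p̄(1 − p̄)) + 1.2816·√(p0(1 − p0) + p1(1 − p1)/r)]² / d²
- corrected n0 = (n/4)·[1 + √(1 + 2(1 + r)/(n·r·d))]²

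**Step 1: reproduce Table 1.** Take brain/leukemias, 65%, u = 10%. Then n0 = 55,055, n1 = 144,495, r = 2.6246. At RR 1.62, p1 = 0.001296, p̄ = 0.0011592 and d = 0.000496. This gives n = (1.6449 × 0.039987 + 1.2816 × 0.035952)² / 0.000496² ≈ 50,850, corrected to about 53,600, which is just inside the 55,055 available. The exact solution is RR 1.61 (stated 1.62). All 40 cells agree within about 0.02, and power at the stated RRs is 0.900 to 0.919.

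**Step 2: 40%, same pooled contrast.** For u = 10%, n0 = 0.40 × 84,700 = 33,880 and n1 = 0.40 × 222,300 = 88,920. For brain/leukemias, RR 1.81 needs about 34,100 unexposed, so the solution is just above 1.81. Ranges run from the 10% to the 30% unexposed column:

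| Cancer group | Stated, 65% | 40% |
|---|---|---|
| Brain, leukemias | 1.62-1.55 | 1.81-1.72 |
| Non-Hodgkin's lymphoma (NHL) | 1.42-1.37 | 1.54-1.48 |
| Bladder | 1.73-1.65 | 1.97-1.85 |
| Pancreas, stomach | 1.93-1.82 | 2.25-2.09 |
| Liver | 2.11-1.98 | 2.51-2.31 |
| Esophagus, larynx, myeloma | 2.43-2.26 | 2.98-2.71 |

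Power at the stated RRs is 69% to 76% over the 40 cells, or 75% to 78% without the continuity correction: roughly 70-77%. Of the 16 cancers listed, 10 stay below 2.0 at 40%, against 12 at 65% (10% column). At 30% response (10% column) the values are NHL 1.64, bladder 2.16, pancreas/stomach 2.51, liver 2.83 and esophagus/larynx/myeloma 3.42.

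**Step 3: active duty and dependents at 40%, unexposed Lejeune merged into the reference.** The number of Lejeune civilians is not given. Removing an assumed 5,000 to 40,000, with 50,000 Pendleton Marines mailed and u = 10%, gives NHL 1.57-1.60, bladder 2.03-2.08, pancreas/stomach 2.34-2.40, liver 2.61-2.70 and esophagus/larynx/myeloma 3.13-3.24. The pooled values in the same column are 1.54, 1.97, 2.25, 2.51 and 2.98, so the split adds little beyond the lower response.

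**Step 4: the same, with unexposed Lejeune kept apart.** The reference is 0.40 × 50,000 = 20,000. The exposed number 0.40 × 0.80 × 247,000 = 79,040, which still includes civilians and is slightly favourable. The results are brain/leukemias 2.06, bladder 2.27, pancreas/stomach 2.66, liver 3.01 and esophagus/larynx/myeloma 3.68. Here 9 of the 16 cancers exceed 2.0.

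**Step 5: civilians alone.** These figures use 10,000 Pendleton civilians mailed, an assumed 5,000 to 40,000 at Lejeune, u = 10% and Table 1 baseline risks. At 65%, NHL runs from 3.53 to 2.20 and liver from 10.41 to 4.85. At 40%, NHL runs from 4.61 to 2.64 and liver from 15.42 to 6.65.

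**The case against.** The 40% is worded as a floor and as something that may be realistic, and Table 1 labels 65% openly as an assumption. That stands. It softens the conflict but does not remove it, because no figure is shown at any other rate. The panel will also see actual participation, but it has only the 65% table to set beside it.

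Four stronger readings are tempting, and the protocol does not support them:

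- **Table 1 is miscalculated.** It is not; it reproduces on its stated inputs.
- **The sentence about most cancers is false at 40%.** It still holds as a count for the pooled contrast, 10 of 16. It fails for active duty only if unexposed Lejeune residents are kept out of the reference group.
- **Each separate analysis has only its Pendleton sample as reference.** The Data Analysis section merges unexposed Lejeune residents when risks are similar, so Step 4 is one branch of the plan and not the plan itself. For the same reason the Pendleton civilian count sets no hard floor on civilian detectable RRs. Those figures also depend on an unstated Lejeune count and on baseline risks for entry at age 19. If civilians were older, their baseline risks would be higher and their detectable RRs lower.
- **Null results will be judged against Table 1.** The section on interpretation relies on RRs, 90% confidence intervals, dose-response, consistency and bias analyses, and does not mention the table.

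**Conclusion.** The point holds as an inconsistency of assumptions. At 40% participation and the same pooled contrast, detectable RRs rise by about 0.1 for the commoner cancers and by about 0.45 to 0.55 for the rarest group. Power at the stated RRs is roughly 70-77%, not 90%. Pancreas and stomach move above 2.0 in every column.

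For active duty with dependents, the drop in participation does most of the damage if unexposed Lejeune residents join the reference group; keeping them apart costs appreciably more. Civilian-only detectable RRs are much larger, but can be given only as a range. All figures assume the continuity-corrected two-proportion method inferred from the table, together with its baseline risks.

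**What to change.** Recompute Table 1 with 40% participation as the base case and 30% and 65% as the range. Give separate tables for active duty with dependents (50,000 Pendleton Marines mailed) and for civilians (10,000 mailed), each with and without unexposed Lejeune residents in the reference group. For civilians, state the assumed Lejeune count and baseline risks and show a range.

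Label the present table as the 65%, combined-analysis case. Reword the sentence about most cancers so that it names the participation rate and analysis it refers to. Give the expert panel this version.

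The cost is a recalculated table with less favourable figures and one revised sentence. No extra participants are needed.

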From the 1950s through the mid-1980s, persons residing or working at the U.S. Marine Corps Base Camp Lejeune, North Carolina were potentially exposed to drinking water contaminated with volatile organic compounds (VOCs). The heavily contaminated wells were shut down in February 1985.

On January 28, 2008, President Bush signed H.R. 4986: National Defense Authorization Act for Fiscal Year 2008. The Act requires ATSDR to develop a health survey of persons possibly exposed to contaminated drinking water at Camp Lejeune that would collect personal health information. The Act further states that the collection of this health information could provide a basis for further scientific studies of potentially adverse health impacts of exposure to contaminated water at Camp Lejeune. The Act requires the survey to be developed within 120 days of enactment and to be conducted within one year of enactment.

The study population for the morbidity study will include the following: (1) Marine and Navy personnel stationed at Camp Lejeune any time during the period June 1975 to December 1985, (2) civilians who worked at Camp Lejeune anytime during the period December 1972 to December 1985, (3) parents and children (who were born prior to 1986 and who are now adults) included in a 1999-2002 ATSDR survey for whom a current address can be found; and (4) a random sample of active duty and civilian workers who were stationed at Camp Pendleton during June 1975- December 1985 and December 1972-

December 1985, respectively, and were not stationed at Camp Lejeune during the period of drinking water contamination. The morbidity study population will be identified from available data from the Defense Manpower Data Center (DMDC) personnel records and the ATSDR 1999-2002 survey data. DMDC data are not available to identify base locations for active duty personnel before June 1975, and DMDC data for civilian employees are not available before December 1972. Health surveys will be mailed to those for whom a current address can be found. Personal identifier information (i.e., name, date of birth, and social security number [SSN]) will be used to obtain current addresses.

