
supplemented with water from the HP system during some weeks in the summer when water use was high. No organic solvent contamination was detected in the drinking water from the other treatment plants serving the base.

1998 ATSDR Study of Adverse Birth Outcomes (“SGA study”)

The Agency for Toxic Substances and Disease Registry (ATSDR) conducted a study of live births to women who resided in base family housing at time of delivery during the period January 1, 1968 through December 31, 1985. Base family housing records were used to identify maternal residence(s) during pregnancy. Information from the birth certificate was used to determine birth weight and gestational age. The study found that “long-term” TCE exposure from HP water was associated with an elevated risk for SGA (OR=3.9, 90% CI: 1.1, 11.9) only among male infants (ATSDR 1998). Exposure to PCE from TT water was associated with elevated risk for SGA among infants born to mothers aged >35 years (adjusted OR=2.1, 90% CI: 0.9, 4.9) and among mothers with two or more prior fetal losses (adjusted OR=2.5, 90% CI: 1.5, 4.3) (Sonnenfeld et al. 2001).

Current ATSDR Epidemiological Study of Specific Birth Defects and Childhood Leukemia

ATSDR is currently conducting a study of birth defects and childhood cancers in children born from 1968 through 1985 to mothers who resided at the base anytime during their pregnancy. Potential cases were identified by a telephone survey of parents conducted by ATSDR during 1999-2002 and were verified using medical records. The phone survey obtained information about the child’s health, the dates of birth of the mother and father, and the dates the parents resided at Camp Lejeune. In 2003, work began on the historical exposure reconstruction of the TT and HP systems.

A total of 106 cases were reported in the survey: 35 NTD, 42 oral clefts, and 29

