Determining the water quality at residences and workplaces at Camp Lejeune is simplified by the fact that, within each water system, the water was completely mixed so all locations served by a water system received similar levels of contamination. It is therefore only necessary to determine in which broad area of the base the residence or workplace is located. The information from the family housing records (for married active duty personnel), the unit identification codes (for single active duty personnel), the MOS code (for active duty workplaces), and the occupation code (for civilian employees), when combined with the information obtained from command chronologies, discussions with knowledgeable former Marines and current base staff, and survey information provided by the respondent, should be sufficient to identify the area of the base where a residence or workplace was located and to determine which water system served that residence or workplace.

Because of uncertainties and variabilities concerning the amount of water each individual routinely consumed (i.e., by ingestion, inhalation and dermal routes), the source of water in the field, the amount of time an individual routinely spent outside the base or in other parts of the base besides the residence, exposure misclassification bias is likely. This bias should be non-differential, i.e., not associated with disease status. However, non-

differential exposure misclassification can distort exposure-response relationships. One approach to reduce the effects of this bias on the exposure-disease relationship is to compare the group with the most certainty of being the highest exposed to the unexposed group. To assess the possible impact of this bias, sensitivity analyses will be conducted assuming different values for the sensitivity and specificity of the exposure classification.

Morbidity Study Population

Persons eligible for the morbidity study are those with accurate and complete addresses who were:

1. Marines and Navy personnel identified from the DMDC computerized personnel database as having been stationed at Camp Lejeune anytime during the period June 1975- December 1985;
2. civilians identified from the DMDC computerized personnel database as having worked at Camp Lejeune anytime during the period December 1972 to December 1985;
3. respondents and their children (who were born prior to 1986 and who are now adults) included in the 1999-2002 ATSDR survey;

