4. Marines stationed at Camp Pendleton anytime during the period June 1975- December 1985, but who were not at Camp Lejeune anytime during the period of drinking water contamination; and
5. civilians employed at Camp Pendleton anytime during the period December 1972-December 1985 who were not at Camp Lejeune anytime during the period of drinking water contamination.

The study population is defined based on available data indicating at which base

the person was stationed or employed. The DMDC personnel records for active duty Marines and Navy personnel do not have information on where the person was stationed (i.e., the unit code) until June 1975. Therefore, the period, June 1975-December 1985 was chosen for inclusion of active duty personnel. The DMDC personnel records for civilian employees began in December 1972 so the period, December 1972-December 1985 was chosen for civilian employees. There is overlap between Marines and Navy personnel included in the DMDC active duty database and the ATSDR 1999-2002 survey; about 65% of the active duty personnel included in the ATSDR survey are also in the DMDC database.

The Camp Lejeune Community Assistance Panel, as well as the panel of epidemiologists convened by ATSDR in 2008, recommended that an unexposed comparison group similar to the Camp Lejeune population be included in order to enhance the scientific credibility of the study. Camp Pendleton was chosen for the comparison population because the base is similar to Camp Lejeune. Camp Pendleton primarily provides training for Marines residing west of the Mississippi while Camp Lejeune primarily provides training for Marines residing east of the Mississippi, although some Marines receive training at both bases. Camp Pendleton has toxic waste sites just like Camp Lejeune. Additionally, the available personnel records are similar for both bases. The major difference is that Camp Pendleton did not have a contaminated drinking water supply.

Current addresses (and if necessary, current names) for the study population will be obtained using a locator firm. The DMDC data includes name, date of birth and social security number. Most of the respondents to the ATSDR 1999-2002 survey provided

their social security numbers, and dates of birth are available for both parents and the study child. Although pregnant women and prisoners are not specifically targeted under this data collection, they will not be excluded.

Sample Size, Power, and Precision of Risk Estimates

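### The main active-duty analysis pools dependents with active duty personnel on an equal-risk assumption, although the Camp Pendleton reference contains no dependents and no planned step tests or corrects a baseline difference

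*Protocol*

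**What the plan says.** **Who is on the Lejeune side.** Protocol, Morbidity Study Population, item 1 admits "Marines and Navy personnel identified from the DMDC computerized personnel database as having been stationed at Camp Lejeune" from June 1975 to December 1985. Item 3 adds "respondents and their children (who were born prior to 1986 and who are now adults) included in the 1999-2002 ATSDR survey". The Introduction describes the study for which that survey was done as one of "children born from 1968 through 1985 to mothers who resided at the base anytime during their pregnancy".

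**Who is on the Pendleton side.** Item 4 of the same list reads "Marines stationed at Camp Pendleton anytime during the period June 1975- December 1985", and Study Objectives describes "active duty Marines and civilian employees randomly sampled from those stationed or employed at Camp Pendleton", sized at 50,000 Marines and 10,000 civilians. The opening summary is looser: "a random sample of active duty and civilian workers who were stationed at Camp Pendleton". Morbidity Study Design likewise speaks of active duty personnel without naming a branch.

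**How they are analysed.** Data Analysis separates civilians and keeps active duty and dependents in one analysis. It notes that Pendleton has no dependents and then says: "It will be assumed that dependents and active duty personnel with similar residential drinking water exposures (including no exposure) will have similar risks". It plans to look afterwards at whether dependent status modifies the exposure-response relationship. It takes Pendleton as the unexposed group for all comparisons. Lejeune residents without contaminated residential water join that group if their disease risk looks similar. If it does not, an indicator distinguishes them from Pendleton. Confounders enter by a 10% change-in-estimate rule, and further models add well-known risk factors.

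**The concern.** Pendleton was added to supply an unexposed population resembling Lejeune's. For dependents it supplies none. They were not selected into military service, they include spouses and people followed from childhood, and at the exposed end they are compared with Pendleton Marines. If their background rate of a disease differs from that of serving personnel, a rate ratio different from 1 can appear with no effect of the water, or a real effect can be hidden.

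For reproductive outcomes the difference is built in. Mothers who enter through the 1999-2002 survey are there because they had a child after an on-base pregnancy. Pendleton Marines were not chosen that way. Infertility, miscarriage and endometriosis are all study outcomes, so equal baseline risk is least credible there.

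**Working it through.** **1. The plan's own figure.** Table 1 assumes 65% response:

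- Lejeune: 247,000 × 0.65 = 160,550
- Pendleton: 60,000 × 0.65 = 39,000
- unexposed in the 10% column: 39,000 + 16,055 = 55,055, as stated

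A two-proportion calculation with continuity correction (two-sided alpha 0.10, power 90%) reproduces all 40 minimum detectable rate ratios within 0.02. For example, the 0.08% row gives 1.61/1.56/1.55/1.54 against 1.62/1.57/1.56/1.55 stated. The sizing arithmetic is sound. It uses one background rate for everyone, so it does not address group composition.

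**2. The reference for this analysis.** Pendleton Marines responding: 50,000 × 0.65 = 32,500, with no dependents. Unexposed dependents can come only from the Lejeune part of the reference. Across the whole cohort in Table 1 that part is 16,055/55,055 = 29% in the 10% column and 48,165/87,165 = 55% in the 30% column. It is pooled only if its risk looks similar.

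**3. What each planned step can do.**

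| Planned step | What it compares | Baseline, dependents v. active duty? |
|---|---|---|
| Effect modification by dependent status | Exposure-response slopes | Not its stated target, and comes after the main analysis |
| Indicator for unexposed Lejeune | Unexposed Lejeune v. Pendleton | No; it mixes dependents and active duty, and exposed dependents are untouched |
| Pooling of unexposed Lejeune | Their overall risk v. Pendleton | No; dependents are not examined separately |

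**4. Size, as illustration only.** The document gives neither the dependents' share *s* of the exposed group nor their baseline rate *k* relative to active duty. With a true rate ratio of 1 and a Pendleton-only reference, the crude rate ratio is 1 + *s*(*k* − 1).

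| *s* | *k* = 0.5 | 0.7 | 1.5 | 2 |
|---|---|---|---|---|
| 0.05 | 0.975 | 0.985 | 1.025 | 1.05 |
| 0.10 | 0.95 | 0.97 | 1.05 | 1.10 |
| 0.25 | 0.875 | 0.925 | 1.125 | 1.25 |

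Table 1's detectable rate ratios for its commoner cancers (0.16% to 0.24% rows) run from 1.30 to 1.42.

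**5. If unexposed Lejeune members are pooled.** Suppose dependents have the same share *s* among them and they form a fraction *g* of the reference. The crude ratio becomes [1 + *s*(*k* − 1)] / [1 + *gs*(*k* − 1)]. For *s* = 0.25 and *k* = 1.5:

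- *g* = 0.29: 1.125/1.036 = 1.09
- *g* = 0.55: 1.125/1.069 = 1.05

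For *k* = 0.7 the results are 0.925/0.978 = 0.95 and 0.925/0.959 = 0.96. Pooling shrinks the bias but does not remove it.

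**6. The 10% rule.** Data Analysis does not name dependent status as a candidate confounder. If it were one, biases such as 0.97 or 1.05 (*s* = 0.10) would not reach a 10% change and the term could be left out.

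**7. Reproductive outcomes.** One planned miscarriage analysis uses the first pregnancy at the base. For a survey mother with only one on-base pregnancy, that pregnancy ended in the birth that brought her into the survey, so it cannot count as a miscarriage. The selection lowers the dependents' apparent risk. Infertility is affected in the same direction, since these women have conceived. For endometriosis the link is indirect, through infertility.

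**The case against.** The strongest reply is that the model can handle this. Exposure is monthly residential contamination, which varies within Lejeune among active duty and dependents alike. A single regression can therefore estimate an exposure effect and a dependent main effect together, the latter from dependents and active duty at the same Lejeune exposure. A branch term works the same way, and an effect-modification model would ordinarily carry the main effect. This stands. A reader might infer from the missing Pendleton dependents that regression cannot adjust at all. That is true only of a direct contrast with Pendleton. What remains is that the main analysis assumes the term away instead of including it.

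Sex and age might also be thought inseparable from exposure here. The survey collects demographics, the models admit confounders, and age may serve as the time scale, so both can be adjusted where the groups overlap. The document gives no sex split for either base.

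It is tempting to say that Navy personnel are absent from Pendleton. Two sections say Marines and two say active duty. Elsewhere the protocol uses Marines loosely, as in its participation strata for Lejeune, where Navy personnel are eligible. This is a conflict to resolve, not an established exclusion.

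Nor does the separate treatment of civilians show inconsistency. The protocol's reason is that their exposure is at the workplace, and nothing in it ranks that difference against this one.

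Finally, the assumption is openly stated, and a covariate list may sit in a statistical analysis plan that is not shown. The joint analysis and the equal-risk assumption, however, are fixed in the protocol itself.

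**Conclusion.** The point holds for dependents. Followed as written, the main active-duty analysis can carry a baseline difference between dependents and Marines into its rate ratios, and no planned step is aimed at that difference. It is most serious for miscarriage and infertility, where the selection of survey mothers makes equal baseline risk implausible, and by extension for endometriosis.

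The size is unknown. The range of 0.93 to 1.13 rests on assumed shares of 10% to 25%, an assumed baseline ratio of 0.7 to 1.5, no covariate adjustment and a Pendleton-only reference. It lies inside Table 1's smallest detectable rate ratio of 1.30, so for common cancers it would distort an estimate more readily than create a finding. A reader might infer that for breast cancer, cervical cancer or endometriosis the bias reaches the full baseline ratio. That would require dependents to supply nearly all exposed cases and no adjustment to be made, and the document shows neither. The civilian analysis has its own Pendleton civilians and is unaffected.

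**What to change.** In Data Analysis, replace the equal-risk assumption:

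- Make active duty Lejeune versus active duty Pendleton the primary contrast.
- Analyse dependents separately, with residentially unexposed Lejeune dependents as reference. The protocol's main reason for needing Pendleton is possible field-water exposure of active duty personnel in training, which does not apply to dependents. For reproductive outcomes this also puts survey-selected mothers on both sides.
- Treat any pooled analysis as secondary. Include main-effect terms for dependent status and branch, kept regardless of the 10% rule and estimated from exposure variation within Lejeune.
- Reconcile the opening summary and Morbidity Study Design with Study Objectives and Morbidity Study Population on whether Navy personnel are sampled at Pendleton. If they are not, restrict the primary contrast to Marines or include a branch term.

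The cost is one more model per disease and some loss of precision for dependents, whose reference group is smaller. The separate dependent analysis and the added terms use data the study already plans to collect, and the mailing total need not change.
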